7.0 Primary and Secondary Endpoint(s) and Associated Hypotheses

7.1 **Primary Endpoints**

The primary safety endpoint for this study is the incidence of early-onset (within 7 days of the ablation procedure) primary AEs. Pulmonary vein (PV) stenosis or atrio-esophageal fistula that occurs greater than one week (7 days) post-procedure shall be deemed a Primary AE.

The primary effectiveness endpoint is defined as freedom from documented symptomatic AF/AT/AFL based on electrocardiographic data during the effectiveness evaluation period (Day 91-365). Additionally, if a subject meets the failure mode criteria (see protocol section 8.2), the subject will be considered as chronic effectiveness failure.

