9.4 Pre-Procedure (Baseline) Assessments

An electronic screening log maintained at the clinical site will be used to document all patients who were reviewed for potential inclusion into the study.

Patients who sign the Patient Informed Consent Form and are randomized **will be considered part of the Main Study.** No patient will be randomized for study participation or treated with the Study Device without having first signed the approved Patient Informed Consent Form.

At each study site committed to participate in the Subpopulation Neurological Assessments (SNA) and after completion of the Calibration Roll-In Phase, consecutively eligible subjects who satisfy SNA exclusion criteria and who sign a unique SNA Patient Informed Consent Form will undergo a cerebral MRI and a general neurological assessment (including the administration of the NIHSS, mRS, MoCA) conducted by a neurologist certified in the administration of the NIHSS and mRS. All baseline neurological assessments must be completed within a 72-hour period leading up to ablation therapy. Ablation therapy will be according to the Main Study randomization.

Following enrollment, but prior to the EP procedure, information will be collected regarding the presenting illness, medical history, and current/past medical therapy.

Pre-procedure assessments are required within the time specified in Table 9.4.A.

Table 9.4A: Baseline (Pre-Ablation) Evaluations and Completion Timeframe

Baseline (Pre-Ablation) Assessment	Completion Timeframe
Transthoracic Echo (TTE) 
 Assess LA size and EF% to confirm eligibility. 	Within 30 days PRIOR to Ablation Procedure
CT/MRA 
 Assess baseline PV diameters to evaluate post-ablation PV narrowing or stenosis. 	Within 30 days PRIOR to Ablation Procedure

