9.9 Summary of Subject Assessment

At each visit, the following assessments should be performed:

Table 9.9A: Summary of Subject Assessments

Assessments	BL	D/C	D7	M1 D7-42	M3 D70-110	M6 D150-210 M9 D235-315	M12 D316-405	UNS	Y2 ±45D Y3 ±45D
Clinic visit	•			•	•	•	•	•	
Patient Information (Demographics) and Consent	•								
Medical history	•								
Pregnancy Test ¹	•								
TTE ²	•	•							
Imaging for detection of LA thrombus (e.g., TEE, ICE, CT, MRI) ³	•								
ECG ⁴	•	•		•	•	•	•	•	
TTM ³					•	•	•	•	
CT/MRA nMARQ GROUP ONLY	• ⁶				•				
Cardiac medication	•			•	•	•	•	•	
Adverse events	•	•	• ⁷	•	•	•	•	•	• ⁷
AFL/AT/AF recurrence and repeat ablation				•	•	•	•	•	• ⁷
CCS-SAF Scale	•				•	•	•		
Cerebral MRI ⁸	• ⁹	• ¹⁰		• ¹¹	• ¹¹	• ¹¹	• ¹¹	• ¹²	
Neurological Exam ⁸	• ⁹	• ¹⁰		• ¹¹	• ¹¹	• ¹¹	• ¹¹	• ¹²	
NIH Stroke Scale ⁸	• ⁹	• ¹⁰		• ¹¹	• ¹¹	• ¹¹	• ¹¹	• ¹²	
mRS	• ⁹				•				
MoCA	• ⁹			•	• ¹¹	• ¹¹	• ¹¹	• ¹²	

1. In all women of child-bearing age and potential. To be completed within 24 hours prior to ablation procedure.
2. Completed within 30 days prior to ablation period.
3. To be completed the day before or the day of the ablation procedure.
4. To be collected if completed as standard of care.

5. Dispensation of TTM device at Month 3.
6. Within 30 days prior to ablation procedure.
7. To be assessed via phone follow-up.
8. Only for SNA subjects.
9. To be performed within 72 hours prior to ablation procedure.
10. To be completed within 72 hours post-ablation procedure.
11. To be undertaken if neurologic symptoms and/or cerebral ischemic lesions identified in a prior evaluation.
12. To be completed only if: (i) a previously mandated test was missed; or, (ii) subject reports neurologic difficulties between scheduled follow-up visits and unscheduled assessment per investigator approval.

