9.10 Descriptions of Procedures

12-lead Electrocardiogram (ECG) – Standard of Care

Data from 12-lead ECG recordings will be collected as described in Table 9.9A. Data from unscheduled ECG's between two consecutive follow-up visits will be collected and reported on the appropriate eCRF (i.e., unscheduled visit eCRF). Copies of ECG reports should be filed in the subject's medical chart with the participating investigator.

Arrhythmia Monitoring - Standard of Care

Additional arrhythmia monitoring data will be collected if standard of care (e.g., Holter monitoring).

Cardiac Computed Tomography (CT) / Magnetic Resonance Angiogram (MRA) – nMARQ (TEST) GROUP ONLY

A cardiac multi slice CT or MRA must be performed according to requirements in Table 9.9A. For each nMARQ subject, the same imaging technique (CT or MRA) should be used pre-ablation and post-ablation, and the exam must follow the CT/MRA protocol supplied by the core lab. Pre-ablation and post-ablation CT/MRAs will be analyzed by a core lab to evaluate PV Stenosis.

Cardiac Medication

All cardiac medications and the indication for which they are prescribed will be documented in subject charts and reported on the appropriate eCRF(s). If an AE is related to intake of medications, details must be provided on the appropriate eCRF(s).

CCS-SAF scale (Dorian *et al.*, 2006)

Subjects will be classified by the physicians (on the eCRF) according to the CCS-SAF scale pre-ablation, and at the 3, 6, 9 and 12 month follow-up visits.

Pregnancy Test

A pregnancy test must be obtained within 24 hours prior to the ablation procedure for ALL female patients of child-bearing age and potential.

Transtelephonic Monitoring (TTM)

Each subject will be provided with a TTM device at the 3-month follow-up visit. Transmissions will be required monthly beginning on Day 91 from their index ablation procedure per the following schedule:

- A minimum of 1 transmission per month will be required beginning Day 91 (following completion of the 3 month blanking period) through the 12-month follow-up visit.
- Additionally, any symptom-triggered episode that occurs from the end of the blanking period through the 12-month follow-up visit should be recorded and transmitted. The core lab representative receiving the transmission will ask the subject to report arrhythmia-related symptoms experienced during each recording.

Transesophageal Echocardiography (TEE)

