Pneumothorax	Adverse event resulting in air introduction into the pleural cavity of the chest between the lung and the chest wall necessitating chest tube placement or surgical intervention.
Heart Block	Impairment of AV conduction requiring intervention due to inappropriate RF application.
Pulmonary Vein Stenosis*	≥70% diameter reduction of pulmonary vein from baseline CT/MRA scan.
Pulmonary Edema (Respiratory Insufficiency)	Respiratory insufficiency resulting in pulmonary complications necessitating intubation or other significant intervention (including diuretics administered specifically for treating pulmonary edema): 
 Pneumonia – infiltrate, fever and leukocytosis ARDS Pulmonary edema

Primary Adverse Event	Description/Criteria
Pericarditis	Major: results in effusion which leads to hemodynamic compromise or requires pericardiocentesis, prolongs hospitalization by more than 48 hours, requires hospitalization or persists for more than 30 days after ablation.
Hospitalization (initial and prolonged)	Adverse event resulting in admission to the hospital or prolongation of expected hospital stay due to an AF ablation procedure or a study device-related cause. Excludes hospitalization solely due to arrhythmia recurrence or non-medically urgent cardioversion.
Vascular Access Complication	Vascular access complication (e.g., groin hematoma, AV fistula, pseudoaneurysm) requiring intervention (e.g., surgical repair, blood transfusion) or admission or prolonged hospitalization.

* Atrio-esophageal fistula and pulmonary vein stenosis that occur greater than one week (7 days) post-procedure shall be deemed Primary AE.

† Hemodynamic compromise or instability is defined as Systolic BP <80 mmHg.

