9.2 As-Treated Population (AT)

The AT subject population will include all randomized patients who have the ablation catheter inserted. They will be categorized by the treatment received if this deviates from the treatment randomized. Calibration Roll-in cases will not be included.

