12.4.1 Primary Safety Endpoints

The incidence of early-onset Primary Adverse Events is the percentage of patients with at least one primary adverse event with onset on Day 0 through Day 7 except for pulmonary vein (PV) stenosis and atrio-esophageal fistula that could occur greater than one week (7 days) post-procedure. The number of primary adverse events (PAE) and the number of subjects experiencing primary adverse events will be reported.

The primary safety outcomes will be presented in the SP, AT populations and for Calibration Roll-in subjects. Listing of PAEs will be provided for subjects in SP.

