12.4.2 Secondary Safety Endpoints

• Incidence of AEs and Serious (Non-Primary) AEs during 12 Month Follow-up

Incidence of Serious Non-Primary AEs and All AEs during the 12 months follow-up will be reported by coded AE categories in three timeframes (ablation to \leq 7 days, \geq 7 to 30 days post ablation and \geq 30 days). AEs will be evaluated by causality and treatment groups using descriptive statistics.

The primary safety outcomes will be presented in the SP, AT populations and for Calibration Roll-in subjects. Listing of will be provided for subjects in the SP.

• PV Stenosis at 3 Months Post Ablation

Incidence of PV narrowing 3 months post ablation (<50%, 50-70%, ≥70% diameter reduction in diameter of pulmonary vein from baseline CT/MRA scan) will be reported overall and by

ablation targets. The percent of subjects with PV narrowing for subjects undergoing an RF ablation procedure using nMARQ system will be presented descriptively.

The outcomes of 3-month PV narrowing will be presented in the ITT subjects in the nMARQ group and for Calibration Roll-in subjects.

• Incidence of AEs and Serious (Non-Primary) AEs during 2nd and 3rd Year Follow-up

All AEs, including Serious Non-Primary AEs and Non-serious AEs, during the 2nd (366-730 days post the index procedure) and 3rd year (>730 days post the index procedure) follow-up period will be summarized by coded AE categories, causality, timeframes and treatment groups using descriptive statistics.

The outcomes of 2nd- and 3rd-year (S)AEs will be presented in the SP, AT populations and for Calibration Roll-in subjects. Listing will be provided for subjects in the SP.

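### Late PV stenosis counts toward the primary safety rate in both arms, but only nMARQ subjects have a scheduled Month-3 CT/MRA; SAP 12.4.1 should say so and show the rate without scan-detected cases

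*SAP*

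**What the plan says.** **Endpoint.** SAP 7.1 defines the primary safety endpoint as early-onset primary adverse events and adds: "Pulmonary vein (PV) stenosis or atrio-esophageal fistula that occurs greater than one week (7 days) post-procedure shall be deemed a Primary AE". SAP 12.4.1 applies a Day 0 to Day 7 window "except for pulmonary vein (PV) stenosis and atrio-esophageal fistula that could occur greater than one week (7 days) post-procedure". Neither limits this to one arm, and nor does Protocol 8.1.

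**Case definition.** Protocol Table 10.1.3A defines PV stenosis as "≥70% diameter reduction of pulmonary vein from baseline CT/MRA scan".

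**Imaging.** The row in Protocol Table 9.9A reads "CT/MRA nMARQ GROUP ONLY", with marks at baseline and Month 3; SAP 6.0 repeats it. Protocol 9.10 says: "For each nMARQ subject, the same imaging technique (CT or MRA) should be used pre-ablation and post-ablation". A core laboratory reads the scans. No section schedules a Month-3 PV scan for control subjects.

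**Presentation.** SAP 12.4.1 reports the primary outcome in the as-treated and safety populations and for Roll-in subjects. SAP 9.2 says of as-treated subjects: "They will be categorized by the treatment received if this deviates from the treatment randomized". SAP 9.4 also groups by treatment received and includes Roll-in subjects. SAP 12.4 gives two-sided 95% intervals and leaves out subjects whose outcome is missing. SAP 8.0 allows no hypothesis test, and SAP 12.7 plans no sensitivity analysis.

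**Separate narrowing table.** SAP 12.4.2: "The outcomes of 3-month PV narrowing will be presented in the ITT subjects in the nMARQ group and for Calibration Roll-in subjects".

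**Baseline scan.** Protocol Table 9.4A lists CT/MRA before ablation, with the purpose "Assess baseline PV diameters to evaluate post-ablation PV narrowing or stenosis" and no arm restriction.

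**The concern.** One component of the composite rests on imaging, and that imaging is scheduled in one arm only. A symptomatic stenosis can come to light in either arm through adverse event reporting and a clinically driven scan. A severe stenosis without symptoms will be looked for systematically only in nMARQ. When the two primary event rates are set side by side, part of any excess in nMARQ could come from the scan rather than the device, and nothing in SAP 12.4.1 warns the reader.

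With efficacy not reported (SAP 12.0), safety is the main outcome content of the final report. At stake is how the descriptive rates and intervals are read.

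**Working it through.** **1. The plan's own figures.** Protocol 11.3.1 and SAP 10.0 assume an 8.6% primary event rate in both arms and give 87.4% safety power for an 8-point margin at a mean size of 417. A fixed-size check with one-sided alpha 1 − 0.9675 = 0.0325 and 208.5 per arm gives:

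- SE = √(2 × 0.086 × 0.914 / 208.5) = 0.02746
- 0.08 / 0.02746 − 1.845 = 1.068, so power is about 85.7%

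This is close to 87.4% but not an exact replication, because the design is adaptive and the simulation appendix is not supplied. Only the 8.6% is used below; the test itself no longer applies.

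**2. Can the added rate be zero?** Protocol 3.3.3 reports no stenosis above 70% on baseline and post-ablation CT/MRA in REVOLUTION. Assuming that all 160 evaluable subjects were imaged, the upper 95% limits for 0/160 are:

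- one-sided: 1 − 0.05^(1/160) = 1.9%
- two-sided: 1 − 0.025^(1/160) = 2.3%

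So zero is compatible with the data, and so is a rate of up to about 2%.

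**3. Points added to the nMARQ rate.** Let s be the rate of severe stenosis found only because of the scan. Assuming independence from the other primary events, the added rate is s × (1 − 0.086). The values of s are assumptions. The 1.3% (persistent) and 3.4% (serious) are background rates in Protocol 4.1, which does not say that those cases were silent or met the 70% threshold. The 3.4% also lies above the REVOLUTION limit and is shown only as an outer edge.

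| s | Points added | nMARQ reads (control 8.6%) | Extra subjects, 125 to 150 per arm |
|---|---|---|---|
| 0 | 0 | 8.6% | 0 |
| 1.3% | 1.2 | 9.8% | 1.5 to 1.8 |
| 2.3% | 2.1 | 10.7% | 2.6 to 3.1 |
| 3.4% | 3.1 | 11.7% | 3.9 to 4.7 |

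The final as-treated size is not given. SAP 12.5 says that 250 ITT subjects were reached, and SAP 3.2 that the look at 300 was cancelled, so 125 to 150 per arm is assumed. At s = 1.3% the chance of no extra case at all is (1 − 0.0119)^125 = 22% to (1 − 0.0119)^150 = 17%.

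**4. Effect on a printed row.** Two extra cases, with exact 95% intervals:

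- 11/125 = 8.8% (4.5 to 15.2) becomes 13/125 = 10.4% (5.7 to 17.1)
- 13/150 = 8.7% (4.7 to 14.4) becomes 15/150 = 10.0% (5.7 to 16.0)

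**5. Safety population.** Roll-in subjects add to nMARQ only. Their final number is not given; the planning figures in Protocol 6.4 are 150 and 250. The nMARQ denominator is then 125 + 150 = 275 to 150 + 250 = 400, and 0.0119 of that is 3.3 to 4.8 subjects.

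**6. Denominators.** SAP 12.4 drops subjects with missing outcomes but does not say whether an nMARQ subject with no Month-3 scan has a missing primary outcome. If such subjects are dropped when event-free, only the nMARQ denominator shrinks and its rate rises further.

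**7. What a second row can show.** Suppose the true silent rates are 1% in nMARQ and 2% in control, a difference of −1 point. The planned row shows +1. A row without scan-detected cases shows 0. Neither is right, and the two do not enclose −1.

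**The case against.** **The SAP already discloses the imaging.** SAP 6.0 prints the nMARQ-only row, and SAP 12.4.2 confines the narrowing table, with its category of 70% or more, to nMARQ and Roll-in subjects. This stands: a reader might infer that the SAP is silent on the matter, and it is not. What is missing is the link to the primary rates in 12.4.1.

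**The information can be pieced together.** Primary events are listed for the safety population, and the narrowing table counts severe cases. This stands in part. The listing lets a reader find stenosis events, but neither output gives the composite rate and interval without scan-detected cases. The narrowing table also uses ITT subjects, not the as-treated or safety population. The table shells (SAP Appendix A) are not supplied and may already hold such a breakdown.

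**An added row has its own bias.** It would come after unblinding (SAP 5.3), run against SAP 12.7, and tend to favour nMARQ, because a scan may find a case before symptoms would. This stands, and is why the row must be secondary and carry that caveat.

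**Nothing is decided by the rate.** The study was terminated, the report resembles an annual progress report, and there is no test. This stands and sets the severity.

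**Unscanned subjects.** A reader might assume that subjects without a scan and without a reported stenosis count as event-free. The SAP contains no such rule, and SAP 12.4 may imply the opposite, so a footnote should not say it.

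**Conclusion.** The point holds as a minor reporting matter. Followed as written, SAP 12.4.1 gives primary event rates by treatment received in which one component is sought by scheduled imaging in one arm only. The other components, including late atrio-esophageal fistula, do not depend on that scan.

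The size is not fixed by the documents. It is zero if scanning found no silent severe case, and about 1 to 2 points under assumed rates of 1.3% to 2.3%, which rest on an assumed arm size and the planning rate of 8.6%.

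Three stronger readings are not supported. A reader might infer that the imbalance could produce a false safety success; scheduled scanning can only raise the nMARQ rate. A reader might infer that the protocol's non-inferiority claim or its power is compromised; SAP 2.0 supersedes the protocol's methods and SAP 8.0 runs no test. A reader might infer that late stenosis cannot be counted in control subjects; it can be reported when it is clinically detected.

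The disagreement between Table 9.4A and Table 9.9A with Section 9.10 on baseline CT/MRA is a separate inconsistency. Since the case definition refers to a baseline scan, the report should be clear about who had one.

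**What to change.** Keep the primary endpoint as defined. In SAP 12.4.1:

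1. Footnote the primary rates: *Month-3 CT/MRA was scheduled in nMARQ subjects only.*
2. State how the missing-outcome rule of SAP 12.4 applies to nMARQ subjects with no Month-3 scan, and use the same denominators in both rows.
3. Add one descriptive row by treatment received, for the as-treated population and for the safety population with Roll-in subjects identified. It gives the primary event rate and exact 95% interval without PV stenosis first detected on the scheduled Month-3 scan. If route of detection was not recorded, leave out PV stenosis with onset after Day 7 in both arms and report the number left out per arm.
4. Label the row as added after unblinding, secondary to the primary rate, and an exception to SAP 12.7. Say that it may undercount nMARQ and that the two rows do not bracket the true difference.

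If the Appendix A shells already give this breakdown, only items 1 and 2 are needed. Separately, reconcile Table 9.4A with Table 9.9A and Section 9.10; with enrollment closed this affects reporting only.

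The cost is one row, one footnote, one sentence on missing scans, and a detection flag where that was recorded (onset dates otherwise). No imaging is added. The drawback is a post-unblinding figure that can favour nMARQ; the fallback in item 3 also removes symptomatic late cases.

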7.2 Secondary Endpoints

Acute Effectiveness:

• Acute effectiveness is defined as complete PVI confirmation as documented by confirmed entrance block (i.e., complete PVI with or without the use of the toolkit's focal catheter).

One-Year Effectiveness:

• Freedom from AF/AFL/AT off antiarrhythmic drug therapy as assessed from the end of the 3-month blanking period to 12 months following the ablation procedure.

Long-Term Effectiveness:

- Freedom from AF/AFL/AT off antiarrhythmic drug therapy as assessed from the end of the 3-month blanking period to 2 year following the ablation procedure.
- Freedom from AF/AFL/AT off antiarrhythmic drug therapy as assessed from the end of the 3-month blanking period to 3 year following the ablation procedure.

Long Term Safety:

- Incidence of AEs and serious adverse events (SAEs) during the 12 month follow-up period post ablation procedure.
- Assessment of PV stenosis at 3 months post-ablation.
- Incidence of AEs and serious adverse events (SAEs) during the 2nd and 3rd year follow-up period post ablation procedure.

7.3 Additional Endpoints

- % PV isolation by study devices, by subject and by PV
- Repeat ablation rate (for AF/AFL/AT)
- Cardiac specific hospitalization rate
- Total fluoroscopy time
- Overall procedure time
- Ablation procedure related parameters
- Device use per targeted PV

7.4 Subpopulation Neurological Assessment (SNA) Endpoints

- Incidence of symptomatic and asymptomatic cerebral emboli pre- and post-ablation.
- Frequency, anatomic location, and size (diameter and volume) of cerebral emboli by MRI testing at baseline, post-ablation and during follow-up (if lesions observed).
- Incidence of new or worsening neurologic deficits, post-ablation and during follow-up.
- NIHSS score, Montreal Cognitive Assessment and Modified Rankin Scale pre- and postablation and during follow-up.

8.0 Level of Significance

Per Closeout Plan, no formal statistical hypothesis and inferential statistics will be formulated and performed for study endpoints. Two-sided 95% confidence intervals will be constructed for the safety endpoints.

9.0 Analysis Sets

The following analyses populations will be used to complete the analyses of the data:

9.1 Intent-to-Treat Population (ITT)

The ITT subject population will include all randomized patients who have the ablation catheter inserted. They will be analyzed as randomized. Lost-to-follow-up and withdrawn / early termination subjects post randomization are included in the ITT population. Calibration Roll-in cases will not be included.

9.2 As-Treated Population (AT)

The AT subject population will include all randomized patients who have the ablation catheter inserted. They will be categorized by the treatment received if this deviates from the treatment randomized. Calibration Roll-in cases will not be included.

9.3 Per Protocol Population (PP)

The PP subject population will include randomized subjects who satisfy the following criteria. Calibration Roll-in subjects will not be included.

- have undergone RF ablation,
- are treated with the study catheters as randomized (nMARQ or TC),
- are in compliance (no major protocol deviations) with the study protocol, and
- have been treated for the study-related arrhythmia.

